5.0 Special Considerations

5.1 Health Insurance Portability and Accountability Act (HIPAA)

The Informed Consent Form will incorporate wording that complies with relevant data protection and privacy legislation. In accordance with the Health Information Portability and Accountability Act (HIPAA), the written Informed Consent Form must include a participant authorization to release medical information to a regulatory authority, or Institutional Review Board (IRB), to grant access to participant's medical information that includes all hospital records relevant to the study, including participants' medical history.

The core elements included in the HIPAA authorization are:

- A description of the information to be used or disclosed that identifies the information in a specific and meaningful fashion;
- The name or other specific identification of the person(s), or class of persons, authorized to make the requested use or disclosure;
- The name or other specific identification of the person(s), or class of persons, to whom the covered entity may make the requested use or disclosure;
- A description of each purpose of the requested use or disclosure;
- An expiration date or an expiration event that relates to the individual or the purpose of the use or disclosure;
- Signature of the individual and date.

5.2 Family Educational Rights and Privacy Act (FERPA) N/A

- 5.3 Code of Federal Regulations Title 45 Part 46 (Vulnerable Populations) N/A
- 5.4 General Data Protection Regulation (GDPR) N/A
- 5.5 NJ Access to Medical Research Act (Surrogate Consent) N/A

6.0 Data Management Plan

6.1 Data Analysis

We will follow intention-to-treat principles and analyze the groups as randomized. A summary table of baseline variables will be created with means and standard deviations for continuous variables or percentages for categorical variables, all stratified by treatment group.

Primary outcome. We will have repeated measures of log10 VL for each participant. These measurements will occur on day 0 (baseline) and at about days 3, 6 and 10. We will fit a linear mixed effects model, where log10 VL is the outcome, indicators for treatment group (SoC reference), time, and treatment by time interactions are the predictors. The model will include a random slope and intercept, to account for within participant correlation. The robust sandwich variance will be used to estimate standard errors. Because we are estimating within participant changes over time from randomization, we can estimate a treatment effect at any particular day. Our primary hypotheses involve the change over time, which we will assess with the treatment by time interaction terms. If participants drop out from the study

before the day 10 visit, we will use all of their preceding data. Linear mixed effects models rely on the assumption that missing data are missing at random.

Secondary outcomes. For binary outcomes, such as progression to having symptoms, intubation, death, hospitalization, and admission to intensive care unit, we will fit logistic regression models. The covariates will include the treatment group indicators. We will report odds ratios and 95% confidence intervals. For change variables, such as change in viral shedding or change in Q-T interval, we will fit linear mixed effects models (similar to primary outcome).

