 Adverse Events Based on Signs and Symptoms When collecting AEs, the recording of diagnoses is preferred (when possible) to recording a list of signs and symptoms. However, if a diagnosis is known and there are other signs or symptoms that are not generally part of the diagnosis, the diagnosis and each sign or symptom will be recorded separately.

D. Data Points

Case Report Forms

Completion of the electronic case report forms (eCRFs) will be done in accordance with the instructions outlined in the study specific data capture plan. All eCRFs are considered the primary

data collection document for the study and are stored in REDCap in a confidential format. Only key personnel who are delegated in the delegation of authority log are permitted to make entries, changes, or corrections in the eCRF. All users will complete user training, as required or appropriate per regulations. An audit trail will be maintained automatically by the electronic CRF management system.

Data Points to be collected:

- Baseline medical history
- Treatment compliance
- Daily temperatures
- Symptoms of disease
- Adverse events
- Concomitant medications
- Any standard of care treatments or procedures to manage COVID-19
- Viral load from saliva specimen
- Viral load from mid-turbinate self-nasal swab
- SARS-CoV-2 infections confirmed or suspected in household members

Data Submission Timeline and Forms

Completion of eCRFs will occur within 72 hours of study time point unless otherwise indicated. Baseline (pre-study) eCRFs (e.g., enrollment, medical history, concomitant medications, etc.) will be completed no later than 24 hours after the start of treatment.

E. Study Duration

Study participants will be treated for five (5) days and will then remain on follow-up for up to 28 days after entry into the study. The estimated time to complete the entire study including data analysis is 3-6 months

F. Endpoints

Primary endpoint:

1. Rate of decline in viral load over the 10 days after randomization

Secondary:

- 1. Proportion of participants with virus below LLOQ at day 10
- 2. Proportion of participants asymptomatic at day 10.
- For those who were asymptomatic at baseline: Progression to symptoms--presence or absence of key symptoms: fever ≥ 100.4^o F (38 ^o C); sore throat, cough, shortness of breath, myalgias, vomiting or diarrhea, or change in smell or taste

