1.5 Sample Size Justification

Primary outcome:

Rate of decline in viral load. We expect a gradual decay in viral loads (depending on when in the infection's natural history participants are enrolled. Participants will be detected as being SARS-CoV-2-positive by our screen at varying points in the infection (some early, some late). Based on the 4 manuscripts with measurements, including Hung et al ³¹ and Gautret et al ¹⁹, we can calculate an expected decline rate. One outcome would be a greater than expected fall in viral load in the active arms vs the SoC arm (e.g., 0.3 log₁₀ /day greater decline =0.9 log₁₀ in 3 days).

We will compare rate of decline in viral load Arm 1 (NTZ, RBV + HCQ) to Arm 2 (placebo) with the aim of determining if the combination of NTZ, RBV + HCQ is superior to placebo. We plan to enroll 35 participants in each arm of the trial for a total of 70. We assume data are collected at baseline and 3, 6 and 10 days after enrollment.

Power calculations were obtained from simulated data, where:

- Baseline log10 VL was generated from uniform (3,9) distribution (i.e., at baseline, people were equally likely to have log10 VL anywhere from 3 to 9. This is consistent with Hung et al ³¹
- For the control group, average change per day was set to either -0.3 or -0.4. In Hung et al ³¹ it appears to be about -0.37.
- For the treatment group, the average decline per day was greater (steeper) than the control group by either 0.2 or 0.3. In Hung et al ³¹the difference in slopes appears to be about 0.2
- Within person SD was set to either 0.5 or 1.
- SD of the slope between individuals was set to 0.2. In Hung et al ³¹ the within-group IQR of log10 VL was relatively small, so we do not expect a large amount of variation in slopes between participants.

Power was calculated using the following steps: (1) generate 1000 data sets in each scenario; (2) fit random slope and intercept models to the simulated data; (3) record the proportion of times that the test of the interaction between treatment and slope was rejected.

		treatment effect		
Slope SoC group	SD	-0.2	-0.3	
-0.3	0.5	94	99	
-0.4	0.5	94	99	
-0.3	1	87	99	
-0.4	1	84	99	

Results: Power (%) based on a sample size of 30 per group

In all of these scenarios we would have >80% power to detect a difference in the slope between groups.

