The participant will then come to the study location at [name] to complete final screening for the trial eligibility. P02 will be measured and 6 lead portable electrocardiogram will be performed; if PO2<92% or QT interval is QTc interval > 450 mSEC the participant will be excluded. Females of childbearing potential will have a urine test to confirm that they are not pregnant.

Inclusion Criteria

- 1. Documented SARS-CoV-2 infection by qPCR assay without symptoms or with mild symptoms consistent with COVID-19 performed within the past 7 days
- 2. Age ≥21

Exclusion Criteria

- 1. COVID-19 symptoms requiring hospitalization
- 2. PO2 < 92%
- 3. Short of breath at time of enrollment
- 4. Retinal eye disease
- 5. Known glucose-6 phosphate dehydrogenase (G-6-PD) deficiency
- 6. Known chronic kidney disease, stage 5 or receiving dialysis
- 7. Current use of:
 - Class 3 AAD (amiodarone, dronaderone, dofetilide, sotalol)
 - Class 1A AAD (procainamide, quinidine, disopyramide)
 - Flecainide
 - SSRI: citalopram (Celexa), Escitalopram (Lexapro)
 - chlorpromazine
 - Cilostazol (Pletal)
 - Donepezil (Aricept)
 - Droperidol
 - Fluoconazole
 - Methadone
 - Ondansetron (Zofran)
 - Thioridazine
 - Macrolides (clarithromycin, erythromycin)
 - Fluroquinolones (ciprofloxacin, levofloxacin, moxifloxacin)
 - Tamoxifen citrate
- 8. Pregnancy or women who are breast feeding
- 9. Inability to tolerate oral medications
- 10. Allergy or prior adverse reaction to either hydroxychloroquine sulfate, ribavirin, or nitazoxanide
- 11. Allergy to adhesives
- 12. QTc interval > 450 mSEC for men and women
- 13. History of Torsade de Pointes VT or prior cardiac arrest or congenital long QT interval
- 14. Non-English-speaking

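### The primary slope analysis and its power simulation make no provision for participants already below quantification on day 0, so the power claim above 80% holds only if few are enrolled

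*Combined protocol and SAP*

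**What the plan says.** The primary endpoint (Section 1.3 F) is: "Rate of decline in viral load over the 10 days after randomization". For its analysis, Section 6.1 states: "We will follow intention-to-treat principles and analyze the groups as randomized". The model follows: "We will fit a linear mixed effects model, where log10 VL is the outcome, indicators for treatment group (SoC reference), time, and treatment by time". It is the group-by-time term that carries the primary test, and each participant has a random intercept and slope. The section gives no rule for values below LLOQ at any visit, although below-LLOQ status at day 10 is a secondary endpoint. No LLOQ value appears in the documents.

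The virological entry criterion (Section 4.1) is: "Documented SARS-CoV-2 infection by qPCR assay without symptoms or with mild symptoms consistent with COVID-19 performed within the past 7 days". No positive result or minimum load is required on day 0. Under Section 1.8, swabs are sent to an intermediate facility, batched, and forwarded to the testing laboratory at a frequency not yet set, so the day-0 result cannot screen anyone out. Section 1.5 expects mixed stages of infection: "Participants will be detected as being SARS-CoV-2-positive by our screen at varying points in the infection (some early, some late".

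The simulation behind the sample size assumes: "Baseline log10 VL was generated from uniform (3,9) distribution". Every simulated participant then declines linearly, with no quantification floor. Section 1.5 concludes that power exceeds 80% in all scenarios.

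**The concern.** A rate of decline is informative only where there is quantifiable virus to decline. A participant who cleared most virus between the qualifying test and day 0 has little room to fall in either arm, whatever the drugs do. If such values are entered at a constant, the participant contributes a slope near zero. A share p of these participants scales the average slope difference by about (1 − p). It also widens the between-person slope variance, because slopes become a mixture of zero and a true decline. Both effects cost power on the primary test, and the reported effect is diluted relative to that in participants with measurable virus.

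The simulation cannot show this cost, because every simulated baseline is at least 3 log10 and nobody reaches a floor. With no coding rule in Section 6.1, the handling of these participants would also be decided after their data exist.

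**Working it through.** **Inputs from Section 1.5.** Control slope: "For the control group, average change per day was set to either -0.3 or -0.4". Treatment effect: "the average decline per day was greater (steeper) than the control group by either 0.2 or 0.3". Within-person SD s is 0.5 or 1, and between-person slope SD is 0.2. Visits are days 0, 3, 6 and 10 (mean 4.75, sum of squares about the mean 54.75). Power is tabulated for 30 per arm; 35 per arm are planned. Assumed here: two-sided 5% level (none is stated), no dropout, and the same share p in both arms.

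**Step 1: reproduce the stated power.** With complete balanced data the interaction test amounts to comparing mean per-person slopes. Slope variance is v = 0.2² + s²/54.75, so the SD is 0.211 (s = 0.5) or 0.241 (s = 1). With 30 per arm and effect 0.2, the normal approximation gives 95.6% and 89.4%, and the t distribution gives 95.0% and 88.4%. The plan states 94/94% and 87/84%. At effect 0.3 the recomputation gives 99.7–100%, against a stated 99%. The 84% cell is about 4 points below the recomputation, on the conservative side. The claim of more than 80% in all scenarios reproduces under the plan's own assumptions.

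**Step 2: add a share p with flat profiles.** With control slope b and effect size e (treated slope b − e):
- mean difference = (1 − p)e
- control slope variance = (1 − p)v + p(1 − p)b²
- treated slope variance = (1 − p)v + p(1 − p)(b − e)²

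Example: n = 35, b = −0.4, s = 1, e = 0.2, p = 0.10.
- v = 0.04 + 1/54.75 = 0.0583
- control variance = 0.9 × 0.0583 + 0.09 × 0.16 = 0.0668
- treated variance = 0.9 × 0.0583 + 0.09 × 0.36 = 0.0848
- SE = √((0.0668 + 0.0848)/35) = 0.0658
- 0.18/0.0658 = 2.73, so power = Φ(2.73 − 1.96) = 78%

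Power (%) at effect 0.2 with 35 per arm, and the share at which power falls to 80%:

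| Control slope | SD | p = 0 | 5% | 10% | 15% | 20% | 30% | 80% crossing, n = 35 | 80% crossing, n = 30 |
|---|---|---|---|---|---|---|---|---|---|
| −0.3 | 0.5 | 97.7 | 94.3 | 89.2 | 83.0 | 76.1 | 62.0 | 17.3% | 13.0% |
| −0.3 | 1 | 93.4 | 88.4 | 82.5 | 76.0 | 69.3 | 56.3 | 12.0% | 7.4% |
| −0.4 | 0.5 | 97.7 | 92.5 | 84.8 | 76.1 | 67.3 | 51.6 | 12.8% | 9.5% |
| −0.4 | 1 | 93.4 | 86.3 | 78.1 | 69.6 | 61.5 | 47.5 | 8.9% | 5.5% |

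The average slope difference falls from 0.20 to 0.18, 0.16 and 0.14 at shares of 10%, 20% and 30%. A fitted mixed model at p = 20% (last row) gave 62%, against 61.5% from the formula. At effect 0.3 the crossings are 27.1–36.7% with 35 per arm and 22.9–32.1% with 30.

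**Step 3: apply the floor at every visit.** In the plan's model, a participant starting at 3 log10 with slope −0.6 reaches 3 − 0.6 × 10 = −3 log10 by day 10, which no assay would report. Keeping the plan's U(3,9) day-0 loads and flooring all values at an assumed 1 log10 gives power of about 57–86% (n = 35, effect 0.2). An assumed 2 log10 gives about 35–67%.

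**Step 4: does restricting to quantifiable day-0 virus recover the loss?** An illustrative model assumes U(3,9) at the qualifying test, a decline of 0.37 per day, and test age uniform over 0–7 days. It puts 22%, 8% and 1% below an LLOQ of 3, 2 and 1 log10 on day 0. For LLOQ 3, for example, the share is the mean of 0.37d/6 = 0.37 × 3.5/6 = 22%. With the same floor at every visit (n = 35, control slope −0.3, SD 1, effect 0.2):

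| Assumed LLOQ | Power, all randomized | Power, restricted | Slope difference, all | Slope difference, restricted |
|---|---|---|---|---|
| 3 | 18% | 23% | 0.043 | 0.055 |
| 2 | 30% | 35% | 0.065 | 0.072 |
| 1 | 51% | 54% | 0.089 | 0.092 |

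These are simulated values and move by a point or two between runs. Across runs the restriction adds about 1–6 points.

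**The case against.** The strongest reply is that the share is unknown and the planned enrolment has slack. With 35 per arm instead of 30, the worst effect-0.2 scenario tolerates almost 9%. With 35 per arm at effect 0.3, every scenario tolerates about 27%. That stands: a reader might infer that the power claim is broken, but the documents give no share that would establish it. The illustrative shares in Step 4 treat U(3,9) as the load at the qualifying test, whereas Section 1.5 calls it baseline. The viral-negativity figures for control groups in Section 1.2 (12.5% at day 6, 93.3% after 7 days) come from follow-up in other studies, so they do not estimate day-0 negativity here.

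A reader might also infer that intention-to-treat is the mistake, or that these participants cannot show a decline. Neither follows. The all-randomized effect is a legitimate estimand. Flat profiles arise only if undetected values are set to a constant, which Section 6.1 does not say, and someone early in infection could be below LLOQ and then rise.

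Finally, one might expect restriction to restore the design. With a 20% share and 35 per arm (control slope −0.3, SD 1), restricting appears to give 86% power and an estimate of 0.20. That holds only if all later values may fall without limit. Under a consistent floor the gain is small, as Step 4 shows.

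What survives is the missing rule, the direction of the dilution, and a simulation that excludes both features.

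**Conclusion.** The point holds in conditional form. Eligibility allows day-0 values below LLOQ, Section 6.1 does not say how they enter the primary model, and the power in Section 1.5 is computed for a population without them. If they are recorded at a constant, the slope difference shrinks by about (1 − p). At effect 0.2, the claim of more than 80% power in all scenarios fails first at about 5.5% with 30 per arm, or 9% with 35 (about 3 of 35). It fails in all four scenarios by about 17% with 35 (about 6 of 35). Effect 0.2 matters most, because Section 1.5 reads a slope difference of about that size from its cited trial. At effect 0.3 the claim holds to about 27% with 35 per arm, and about 23% with 30.

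These thresholds assume a two-sided 5% level, no dropout, equal shares in both arms, and no floor on later values. Flooring after baseline may cost as much power or more, so a baseline rule is useful but not sufficient.

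**What to change.** 1. **Section 6.1, analysis set.** Define the primary viral-load set as all randomized participants, analysed as randomized, whose day-0 swab was taken before the first dose and is at or above LLOQ. Report the all-randomized analysis alongside it, and keep everyone for clinical and safety endpoints. Restricting on a pre-dose value measured blind to arm is not post-randomization selection. The swab's timing should be stated explicitly: the procedures list in Section 1.3 A puts specimen collection before randomization and dispensing, while Section 1.3 B mentions it after medication is provided.
2. **Section 6.1, values below LLOQ.** State the LLOQ, and use a censored-data likelihood for values below it after baseline, and at every visit in the all-randomized analysis.
3. **Section 1.5.** Rerun the simulation with a range of baseline-negative shares (for example 10–20%) and the same LLOQ at every visit, using the analysis in items 1 and 2, and restate the power.

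The cost is protocol wording and a rerun of the simulation, with no new data. The downside is a primary set somewhat smaller than 70, and a conclusion limited to participants with quantifiable virus on day 0.

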1.0 Research Design

1.1 Purpose/Specific Aims

The purpose of this study is to evaluate the efficacy of Nitazoxanide (NTZ), Ribavirin (RBV) and Hydroxychloroquine (HCQ) versus placebo in participants with proven SARS-CoV-2 infection who are asymptomatic or mildly symptomatic with COVID-19. Those with illness requiring hospitalization, or who present with hypoxia (PO2<92%) or shortness of breath at time of enrollment are excluded.

A. Objectives

In participants with proven SARS-CoV-2 infection who are asymptomatic or mildly symptomatic with COVID-19 randomly allocated to nitazoxanide, ribavirin plus hydroxychloroquine (NTZ, RBV + HCQ) or placebo.

Primary Objective:

To assess the rate of decline in viral load over the 10 days after randomization between participants treated with NTZ, RBV + HCQ for COVID-19 and placebo.

Secondary Objective:

- 1. To compare the proportion of participants with virus below LLOQ at day 10
- 2. To compare the proportion of participants who are asymptomatic and symptomatic at day 10
- 3. To compare the time of onset and frequency of the development of fever and other symptoms of COVID-19 in those who were asymptomatic at enrollment
- 4. To compare the progression in severity of COVID-19 symptoms (hospitalization and length of stay; admission to intensive care unit and number of days in unit; intubation, Death (any cause))
- 5. To compare the severity of disease in participants who develop symptoms of COVID-19
- 6. To compare the side effects of NTZ, RBV + HCQ compared to placebo
- 7. To determine whether baseline viral load predicts response to therapy
- 8. To assess the rate of decline in viral load over days 3 and 6 after randomization
- 9. To assess new, self-reported COVID-19 infection in household members

B. Hypotheses / Research Question(s)

We hypothesize that treatment with NTZ, RBV + HCQ decreases viral load and the progression of symptoms, or emergence of symptoms in those who are asymptomatic at baseline, in SARS-CoV-2-positive adults compared to placebo.

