1.3 Research Design and Methods

We will conduct a randomized clinical trial enrolling eligible participants who are determined to be SARS-CoV-2-positive (e.g., via Rutgers Corona Cohort [RCC] study, hospital or other screening programs) who volunteer for the study. Specifically, we will enroll 70 participants whose test has been performed within the past 7 days who are either asymptomatic or mildly symptomatic at baseline. Mild COVID-19 symptoms include new cough, sore throat, fever, myalgias, new vomiting or diarrheaor change in smell or taste. Illness requiring hospitalization, or those who present with hypoxia (PO2<92%) or shortness of breath at time of enrollment will be classified as significantly symptomatic and excluded from study participation. People who are allergic or intolerant to NTZ, RBV or HCQ will be excluded. We will randomly allocate participants stratified by presence of mild symptoms to 1) NTZ, RBV and HCQ or 2) placebo. Treatment with the investigational agents or placebo will continue for 5 days. Viral load will be assessed at baseline (day 0) as well as at days 3, 6, and 10 to monitor response to antiviral treatment. Immune status will be determined by antibody testing of blood collected at baseline and day 28.

Prior to initiating enrollment, we will prepare two randomization tables for treatment assignment using permuted blocks of six which will be provided to the research pharmacist. One table will be used for participants without symptoms and the other will be used for those with mild symptoms. The pharmacist will prepare kits containing the 5-day supply of study medications (investigational drugs/placebo) which will be sequentially numbered in accordance with the randomization tables. The contents of each kit (investigation drugs/placebo) will be indistinguishable. Study staff will establish symptom status at the baseline visit, and per pharmacy order, provide the participant the next numbered medication kit in the participant's stratum (no symptoms/mild symptoms). The study investigators, staff interacting with the participants are all masked to treatment assignment

A. Research Procedures

- 1. Study Procedures:
 - Day 0/1 Screening/Baseline Visit (in person)
 - Pre-screen via online screening form to confirm eligibility
 - Obtain informed consent for trial enrollment
 - Medical history
 - Medication history
 - Document symptoms (if any)

- o Take temperature, PO2, Pulse
- Q-T interval assessment

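### Randomisation is stratified by baseline symptoms, but no model in section 6.1 names the stratum, so the test of day-10 symptom status is conservative if baseline symptoms are prognostic (minor; free improvement)

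*Combined protocol and SAP*

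**What the plan says.** **Design (section 1.3).** "We will randomly allocate participants stratified by presence of mild symptoms". Two tables with blocks of six are prepared: "One table will be used for participants without symptoms and the other will be used for those with mild symptoms". The stratum is known before a kit is issued, because "Study staff will establish symptom status at the baseline visit".

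**Analysis (section 6.1).** In the primary mixed model, "indicators for treatment group (SoC reference), time, and treatment by time interactions are the predictors"; it has a random intercept and slope and sandwich standard errors. For the logistic models, "The covariates will include the treatment group indicators" and "We will report odds ratios and 95% confidence intervals". This wording does not rule out a stratum term, but it prespecifies none, and I found none elsewhere. Nor does it say whether the odds ratio is marginal or conditional on stratum.

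**Endpoints.** Secondary objective 2 in section 1.1 reads "To compare the proportion of participants who are asymptomatic and symptomatic at day 10". Secondary endpoint 2 in section 1.3 F is "Proportion of participants asymptomatic at day 10" and covers all participants. Endpoint 8 combines undetectable virus with freedom from symptoms and carries no day. Endpoint 3, progression to symptoms, is confined to those without symptoms at baseline.

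**The concern.** Blocking within strata balances the arms on baseline symptoms and so reduces the true variance of the treatment comparison. A model without the stratum still reports the variance that simple randomisation would give. If the stratum predicts the outcome, the reported standard error is larger than the estimator's actual sampling error. The test then rejects too rarely and the interval covers too often.

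This matters most where the stratum is the baseline value of the outcome. That is the case for endpoint 2, and for the symptom part of endpoint 8 if it is assessed when both strata contribute. At stake are the accuracy of the promised 95% intervals and some power, in a trial of 70 where power for such an endpoint may be near one half. For the primary slope, only a difference in the rate of decline between strata would matter, and the documents give none.

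**Working it through.** **1. The plan's own figure (primary slope).** Inputs from section 1.5: visits on days 0, 3, 6 and 10, slope SD 0.2, within-person SD 0.5 or 1, effect 0.2 log10/day, 30 per group. The documents do not state alpha; two-sided 0.05 is assumed throughout.

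- Sxx = (0 + 9 + 36 + 100) - 4 × 4.75² = 54.75.
- At SD 1, the slope variance is 0.04 + 1/54.75 = 0.0583 and the SE of the difference is √(2 × 0.0583/30) = 0.0623. Power is Φ(0.2/0.0623 - 1.96) = 89.4% (88.4% with a t reference). The plan gives 87 and 84.
- At SD 0.5, power is 95.6% (t: 95.0%). The plan gives 94.

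The 84 cell is about 4 points low, and nothing in the stated inputs makes power depend on the control slope. The claim of more than 80% stands, and the discrepancy has no bearing here. The plan gives no figures for endpoints 2 or 8.

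**2. Endpoint 2, closed form.** Let R² = Var(stratum rate)/[p(1-p)]. The actual error of the treatment-only test is 2[1 - Φ(1.96/√(1-R²))]. Assume a 35:35 split. Control rates are written as no symptoms/mild symptoms.

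- 80/50: p = 0.65, R² = 0.0225/0.2275 = 0.099, error 3.9%.
- 90/30: p = 0.60, R² = 0.09/0.24 = 0.375, error 1.3%.
- 70/65: p = 0.675, R² = 0.000625/0.2194 = 0.003, error 5.0%.

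**3. Endpoint 2, simulation.** 20,000 trials of 70 per setting, blocks of six within stratum, Wald tests, within-stratum odds ratio 3.5 for power, 35:35 split. Each pair is treatment only vs with stratum.

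| Control rates | Type I error | Power |
|---|---|---|
| 70/65 | 4.8 vs 5.0% | 51.2 vs 51.5% |
| 80/50 | 3.4 vs 4.7% | 50.1 vs 53.3% |
| 90/30 | 1.2 vs 4.4% | 35.2 vs 49.8% |

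A repeat simulation gave error of 3.6 vs 4.7% (80/50) and 0.8 vs 3.8% (90/30), with power of 50 vs 54% and 37 vs 51%. Coverage at no effect is one minus the error, so about 96.6% and 98.8% from the table. At 80/50 with unequal splits (no symptoms:mild), power is 61.3 vs 63.4% (14:56) and 34.9 vs 38.4% (56:14).

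At 90/40, treatment-only error is 1.9% under stratified randomisation and 4.5% under simple randomisation. Stratifying without adjusting is therefore the main cause.

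**4. What adjustment does to the interval.** Median log-odds-ratio SE at 35:35, for the unadjusted, stratum-conditional and standardised estimates: 0.603, 0.643 and 0.582 at 80/50; 0.542, 0.667 and 0.461 at 90/30. Only standardisation narrows the interval. The conditional odds ratio is also a different quantity. At 90/30 a conditional 3.5 gives active rates of 0.969 and 0.600, mean 0.785, and so a marginal odds ratio of (0.785/0.215)/(0.6/0.4) = 2.43.

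**5. Bias.** With complete data the mean log odds ratio under no effect is about zero in every setting. Suppose instead that 5%/25% (no symptoms/mild) are lost on active and 15%/15% on placebo, with true rates of 80/40 in both arms. The active rate is then (0.95 × 0.8 + 0.75 × 0.4)/1.70 = 0.624 against 0.600, an odds ratio of 1.10. At 90/30 it is 1.16.

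**6. Primary slope.** Let D be an assumed difference in slope between strata, with total slope SD 0.2 and within-person SD 1. At 35:35 the unadjusted SE is too wide by √[0.0583/(0.0583 - 0.25D²)] - 1, which is 2, 10 and 28% at D = 0.1, 0.2 and 0.3. Power without and with stratum and stratum-by-time terms at D = 0, 0.1, 0.2 and 0.3 is 92.8 vs 92.8, 93.1 vs 93.7, 94.2 vs 96.2 and 96.6 vs 99.2%. With about 14% missing by day 10 it runs from 89.7 vs 89.7% to 93.8 vs 98.5%.

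**The case against.** The strongest objection is that the size is wholly assumed. The documents give no day-10 symptom rates, stratum split or effect on symptoms. The loss runs from nothing (70/65) to about 14 points of power (90/30), and they do not say which case applies. That stands, and it is why the point is minor. The prognostic condition is plausible all the same, since symptom status at entry is the baseline value of endpoint 2.

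Second, not all the conservatism comes from the missing stratum. Adjusted error at 90/30 is still 4.4%, or 3.8% in the repeat run, and 2.9% at a 56:14 split. That residue is small-sample Wald behaviour, which a stratum term does not cure.

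A reader might infer more than the documents support:

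- *That the treatment effect is biased or false positives are inflated.* Neither follows. The marginal odds ratio is unbiased with complete data, or when dropout does not differ by stratum and arm together, and the error rate moves downward.
- *That adding the stratum shortens the odds-ratio interval.* In the logistic model it lengthens it. The gain is in error rate and power; the unadjusted interval is too wide only for its own estimator.
- *That there are two day-10 symptom endpoints.* Only endpoint 2 is dated day 10.
- *That the primary analysis is undermined.* Section 1.5 expects little variation in slopes, so a small D is more plausible, and there the gain is under one point.

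**Conclusion.** The omission is real and its direction is certain: if baseline symptoms predict the outcome, the treatment-only logistic analysis of endpoint 2 is conservative. The same applies to endpoint 8 if its assessment day takes in both strata. At 35:35, type I error is about 3.5% at assumed control rates of 80/50 and about 1% at 90/30. The power forgone at an odds ratio of 3.5 is about 3 to 4 points and about 14 points respectively. Nothing is lost if the strata barely differ.

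These sizes rest on assumed rates, split and odds ratio, on two-sided 0.05, and on complete data. Endpoint 3 lies in one stratum and is unaffected. Little power is at stake for the primary test. Severity is minor, and the change is a free improvement.

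**What to change.** Before unblinding, add to section 6.1:

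- The logistic models for endpoint 2, and for endpoint 8 with its assessment day stated, include the symptom stratum.
- Which odds ratio is reported. If the aim is a narrower interval for the marginal effect, report it standardised over the strata. If it is stratum-conditional, say so and note that its log-odds-ratio SE is larger although error rate and power improve.
- A Mantel-Haenszel odds ratio over the strata is used if all participants in a stratum have the same outcome. At odds ratio 3.5 this happens in 0.6% (80/50) or 9.2% (90/30) of simulated trials at 35:35, and in 12.9% or 38.6% at 14:56.

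Stratum and stratum-by-time terms in the primary mixed model are an optional efficiency gain. Endpoint 3 needs no change.

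The cost is one or two sentences, using a variable that staff already establish at baseline. Primary power is not materially reduced: at D = 0 it is 92.8% either way with complete data, and with dropout 89.7% either way at 35:35 and 90.0 vs 89.8% at 14:56. Using Mantel-Haenszel only as the fallback changes power by less than 0.1 point.
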